Appendix 5 The Recommendations for irAE Management

This appendix provides recommendations to the Investigators for the management of irAEs. The contents are based on the NCCN irAE management guidelines (in Accordance with the Joint American Society of Clinical Oncology Clinical Practice Guidelines and National Comprehensive Cancer Network, Brahmer JR, 2018) and FDA recommendations to require permanent treatment discontinuation for Grade 4 irAEs (unless otherwise indicated in the tables below). Differences with ASCO/NCCN irAE management guidelines as recommended by the FDA are shown in bold and underlined text in the tables below. Critical instructions include the requirement that treatment must be permanently discontinued for the following Grade 4 irAEs toxicities: Rash/inflammatory dermatitis, nephritis, autoimmune hemolytic anemia, hemolytic uremic syndrome, aplastic anemia, immune thrombocytopenia, acquired TTP, and in certain circumstances, lymphopenia.

Table of Tables

Table A1	Management of Skin irAEs in Patients Treated With ICPis.....	96
Table A2	Management of GI irAEs in Patients Treated With ICPis.....	101
Table A3	Management of Lung irAEs in Patients Treated With ICPis	105
Table A4	Management of Endocrine irAEs in Patients Treated With ICPis ...	106
Table A5	Management of Musculoskeletal irAEs in Patients Treated With ICPis	111
Table A6	Management of Renal irAEs in Patients Treated With ICPis.....	115
Table A7	Management of Nervous System irAEs in Patients Treated With ICPis	117
Table A8	Management of Hematologic irAEs in Patients Treated With ICPis	122
Table A9	Management of Cardiovascular irAEs in Patients Treated With ICPis	129
Table A10	Management of Ocular irAEs in Patients Treated With ICPis	131

Table A1

Management of Skin irAEs in Patients Treated With ICPis

1.0 Skin Toxicities	
1.1 Rash/inflammatory dermatitis	
Definition: Erythema multiforme minor (a targetoid reaction in the skin and mucous membranes usually triggered by infections, such as herpes simplex viruses, but can be associated with an immune-related drug eruption and if progresses to erythema multiforme major, it and can be a harbinger of SCAR, such as SJS), lichenoid (resembling the flat-topped, polygonal, and sometimes scaly or hypertrophic lesions of lichen-planus), eczematous (inflammatory dermatitis characterized by pruritic, erythematous, scaly, or crusted papules or plaques on the skin, which is vulnerable to superinfection, psoriasisiform [resembling the well-demarcated, erythematous, and scaly papules and plaques of psoriasis], morbilliform [a nonpustular, nonbullous measles-like exanthematous rash of the skin often referred to as "maculopapular" and without systemic symptoms or laboratory abnormalities, excluding occasional isolated peripheral eosinophilia], palmoplantar erythrodysthesia [hand-foot syndrome; redness, numbness, burning, itching, and superficial desquamation of the palms and soles], neutrophilic dermatoses [e.g, Sweet syndrome], and others)	
Diagnostic work-up	
Pertinent history and physical examination Rule out any other etiology of the skin problem, such as an infection, an effect of another drug, or a skin condition linked to another systemic disease or unrelated primary skin disorder If needed, a biologic checkup, including a blood cell count and liver and kidney tests Directed serologic studies if an autoimmune condition is suspected, such as lupus or dermatomyositis: a screening antinuclear antibody test, SS-A/Anti-Ro, SS-B/Anti-La if predominantly photodistributed/photosensitivity, antihistone, double-stranded DNA, and other relevant serologies. Consider expanding serologic studies or diagnostic work-up if other autoimmune conditions are considered based on signs, symptoms Skin biopsy Consider clinical monitoring with use of serial clinical photography Review full list of patient medications to rule out other drug-induced cause for photosensitivity	
Grading	Management
Grading according to CTCAE is a challenge for skin. Instead, severity may be based on BSA, tolerability, morbidity, and duration	
G1: Symptoms do not affect the quality of life or controlled with topical regimen and/or oral antipruritic	Continue ICPi Treat with topical emollients and/or mild-moderate potency topical corticosteroids Counsel patients to avoid skin irritants and sun exposure
G2: Inflammatory reaction that affects quality of life and requires intervention based on diagnosis	Consider holding ICPi and monitor weekly for improvement. If not resolved, interrupt treatment until skin AE has reverted to Grade 1 Consider initiating prednisone (or equivalent) at dosing 1 mg/kg, tapering over at least 4 weeks In addition, treat with topical emollients, oral antihistamines, and medium- to high-potency topical corticosteroids
G3: As G2 but with failure to respond to indicated interventions for a G2 dermatitis	Hold ICPi therapy and consult with dermatology to determine appropriateness of resuming Treat with topical emollients, oral antihistamines, and high-potency topical corticosteroids Initiate (methyl)prednisolone (or equivalent) 1-2 mg/kg, tapering over at least 4 weeks
G4: All severe rashes unmanageable with prior interventions and intolerable	Permanently discontinue ICPi Systemic corticosteroids: IV (methyl)prednisolone (or equivalent) dosed at 1-2 mg/kg with slow tapering when the toxicity resolves

1.0 Skin Toxicities	
	
Monitor closely for progression to severe cutaneous adverse reaction
 
Should admit patient immediately with direct oncology involvement and with an urgent consult by dermatology

1.2 Bullous dermatoses	

Definition: Including bullous pemphigoid or other autoimmune bullous dermatoses, bullous drug reaction
 
Diagnostic work-up
 
Physical examination
 
Rule out any other etiology of the skin problem, such as an infection, an effect of another drug, or a skin condition linked to another systemic disease
 
If needed, a biologic checkup, including a blood cell count, liver, and kidney tests; consider serum antibody tests to rule out bullous pemphigoid or, under the guidance of dermatology, sending patient serum for indirect immunofluorescent testing to rule out other autoimmune blistering diseases
 
Referral to dermatology for blisters that are not explained by infectious or transient other causes (e.g, herpes simplex, herpes zoster, bullous impetigo, bullous insect bite, friction or pressure blister)
 
Consider skin biopsy (both hematoxylin and eosin evaluation of lesional skin and direct immunofluorescence evaluation of perilesional skin)
	
Grading	Management
G1: Asymptomatic, blisters covering < 10% BSA and no associated erythema	
If blisters are < 10% BSA, asymptomatic, and noninflammatory (such as the case with friction blisters or pressure blisters), cessation of ICPi is not necessary, and only observation and/or local wound care is warranted.
 
When symptomatic bullae or erosions, which are deroofed vesicles or bullae, are observed on the skin or mucosal surfaces, the cutaneous irAE is by definition considered at least G2
 
See G2 management recommendations

G2: Blistering that affects quality of life and requires intervention based on diagnosis not meeting criteria for Grade > 2 Blisters covering 10%-30% BSA	
Hold ICPi therapy and consult with dermatology for work-up and to determine appropriateness of resuming
 
Attention given to general local wound care, which includes plain petrolatum ointment and bandages or plain petrolatum ointment gauze and bandage over any open erosions, which are left over on the skin after the blister has popped or if the roof of the blister easily sloughs off
 
Counsel patients to avoid skin irritants and overexposure to sun, wear protective clothing, use sunscreens
 
Work-up for autoimmune bullous disease as above
 
Initiate Class 1 high-potency topical corticosteroid (e.g, clobetasol, betamethasone or equivalent) and reassess every 3 days for progression or improvement
 
Low threshold to initiate treatment with prednisone (or equivalent) at 0.5-1 mg/kg dosing and taper over at least 4 weeks
 
Monitor patients with G2 irAEs closely for progression to involvement of greater BSA and/or mucous membrane involvement. Consider following patients closely using serial photography
 
Primer on monitoring for complicated cutaneous adverse drug reactions:

1.0 Skin Toxicities	
	Review of systems: Skin pain (like a sunburn), fevers, malaise, myalgias, arthralgias, abdominal pain, ocular discomfort or photophobia, sores or discomfort in the nares, sores or discomfort in the oropharynx, odynophagia, hoarseness, dysuria, sores or discomfort in the vaginal area for women or involving the meatus of the penis for men, sores in the perianal area, or pain with bowel movements
	Physical examination: Include vital signs and a full skin examination specifically evaluating all skin surfaces and mucous membranes (eyes, nares, oropharynx, genitals, and perianal area). Assess for lymphadenopathy, facial or distal extremity swelling (may be signs of DIHS/DRESS). Assess for pustules or blisters or erosions in addition to areas of "dusky erythema," which may feel painful to palpation. To assess for a positive Nikolsky sign, place a gloved finger tangentially over erythematous skin and apply friction parallel to the skin surface. Nikolsky sign is positive if this results in detached or sloughing epidermis demonstrating poor attachment of the epidermis to the dermis, which is the case in some autoimmune disorders (eg, pemphigus) and SJS/TEN
G3: Skin sloughing covering > 30% BSA with associated pain and limiting self-care ADL	Hold ICPi therapy and consult with dermatology to determine appropriateness of resuming Administer IV (methyl)prednisolone (or equivalent) 1-2 mg/kg, tapering over at least 4 weeks If bullous pemphigoid is diagnosed, it may be possible to avoid long-term use of systemic corticosteroids and treat with rituximab, as an alternative approach to treating the irAE Seek infectious disease consultation if patient might have secondary cellulitis or if patient has other infection risk factors, such as neutropenia, etc.
G4: Blisters covering > 30% BSA with associated fluid or electrolyte abnormalities	Permanently discontinue ICPi Admit patient immediately and place under supervision of a dermatologist Administer IV (methyl)prednisolone (or equivalent) 1-2 mg/kg with tapering over at least 4 weeks when the toxicity resolves If bullous pemphigoid is diagnosed, it may be possible to avoid long-term use of systemic corticosteroids and treat with rituximab as an alternative approach to treating the irAE Seek infectious disease consultation if patient might have secondary cellulitis or if patient has other infection risk factors, such as neutropenia, etc
1.3 SCARs, including SJS, TEN, acute generalized exanthematous pustulosis, and DRESS/DIHS	
Definition: Severe changes in either structure or functions of skin, the appendages or the mucous membranes due to a drug	
Diagnostic work-up	
Total body skin examination with attention to examining all mucous membranes as well as complete review of systems	
Rule out any other etiology of the skin problem, such as an infection, an effect of another drug, or a skin condition linked to another systemic disease	

1.0 Skin Toxicities

A biologic checkup, including a CBC with differential test, and liver and kidney function tests, including urinalysis, in addition to the blood work; if the patient is febrile, blood cultures should be considered as well

Skin biopsies to assess for full-thickness epidermal necrosis, as is seen in SJS/TEN, as well as other possible etiologies like paraneoplastic pemphigus or other autoimmune blistering dermatoses or other drug reactions, such as acute generalized exanthematous pustulosis

Consider following patients closely using serial clinical photography

If mucous membrane involvement or blistering is observed on the skin, consider early admission to a burn center for further monitoring and management. Primer on monitoring for complicated cutaneous adverse drug reactions:

Review of systems: Skin pain (like a sunburn), fevers, malaise, myalgias, arthralgias, abdominal pain, ocular discomfort or photophobia, sores or discomfort in the nares, sores or discomfort in the oropharynx, odynophagia, hoarseness, dysuria, sores or discomfort in the vaginal area for women or involving the meatus of the penis for men, sores in the perianal area, or pain with bowel movements

Physical examination: Include vital signs and a full skin examination specifically evaluating all skin surfaces and mucous membranes (eyes, nares, oropharynx, genitals, and perianal area). Assess for lymphadenopathy, facial or distal extremity swelling (may be signs of DIHS/DRESS). Assess for pustules or blisters or erosions in addition to areas of "dusky erythema", which may feel painful to palpation. To assess for a positive Nikolsky sign, place a gloved finger tangentially over erythematous skin and apply friction parallel to the skin surface. Nikolsky sign is positive if this results in detached or sloughing epidermis demonstrating poor attachment of the epidermis to the dermis, which is the case in some autoimmune disorders (e.g. pemphigus) and SJS/TEN

Grading	Management
All Grades	In cases of suspected SJS or any mucous membrane involvement, discontinue ICPi treatment and monitor closely for improvement, regardless of grade
G1: NA	For SCARs, there is no G1 category; if lower BSA is involved with bullae or erosions, there should remain a high concern that this reaction will progress to G3 or G4
G2: Morbilliform ("maculopapular") exanthem covering 10%-30% BSA with systemic symptoms, lymphadenopathy, or facial swelling	Hold ICPi and monitor patients closely every 3 days with G2 irAEs for progression to involvement of greater BSA and/or mucous membrane involvement Consider following patients closely using serial photography Initiate therapy with topical emollients, oral antihistamines, and medium- to high-strength topical corticosteroids Consider initiation of prednisone (or equivalent) 0.5-1 mg/kg tapered over at least 4 weeks
G3: Skin sloughing covering < 10% BSA with mucosal involvement associated signs (e.g. erythema, purpura, epidermal detachment, mucous membrane detachment)	Hold ICPi therapy and consult with dermatology Treat skin with topical emollients and other petrolatum emollients, oral antihistamines, and high-strength topical corticosteroids; dimethicone may also be offered as an alternative to petrolatum Administer IV (methyl)prednisolone (or equivalent) 0.5-1 mg/kg and convert to oral corticosteroids on response, wean over at least 4 weeks Admit to burn and/or consult wound services with attention to supportive care, including fluid and electrolyte balance, minimizing insensible water losses, and preventing infection Given the immune mechanism of action of these medicines, use of immune suppression is warranted and should be offered

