6.8 Special Precautions

Any treatment-emergent adverse event (TEAE) that is assessed as potentially related to bintrafusp alfa, may require permanent or transient discontinuation of bintrafusp alfa treatment.

Single laboratory values out of the normal range that do not have any clinical correlation do not necessarily need treatment interruption. Questions or concerns with regard to management and/or follow-up of TEAEs should be discussed with the Medical Monitor.

Immune-related AEs, IRRs including hypersensitivity, anemia, TGF- β inhibition mediated skin reactions, and bleeding events are managed and followed up in their respective sections as indicated below. Permanent study intervention discontinuation may be recommended, so the relevant section must be reviewed:

- For suspected irAEs, general management by NCI-CTCAE v5.0 toxicity grading is listed in Section [6.9.2](#). Recommended guidance and management for specific irAEs as per published guidelines is provided in [Appendix 5](#).
- IRR and hypersensitivity reaction guidance are presented in Section [6.9.1](#).
- Anemia guidance is presented in Section [6.9.4](#).

- Potential TGF- β inhibition mediated skin AEs guidance and management are provided in Section **Error! Reference source not found..**
- Guidance and management of bleeding events are discussed in Section **6.9.5.**

General guidance:

- In any case, if ≥ 2 doses are missed due to AE, the Medical Monitor should be consulted.
- Inability to reduce corticosteroid dose to 10 mg or less of prednisone or equivalent per day within 12 weeks is an indication for permanent treatment discontinuation (except for use of steroids as hormone substitution).
- Persistent Grade 2 or 3 adverse reactions (excluding endocrinopathies controlled with hormone replacement therapy) that do not recover to Grade 0 to 1 within 12 weeks after last dose of study intervention is an indication for permanent treatment discontinuation.

In general, the following applies for TEAEs related to bintrafusp alfa that are not covered by the recommendations for irAE management in [Appendix 5](#):

Grade 4 treatment-related TEAEs

Any Grade 4 treatment-related TEAEs require permanent treatment discontinuation, except:

- Endocrinopathies that have been controlled by hormone replacement,

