1. If a Grade 2 treatment-related TEAE resolves to Grade ≤ 1 by the day before the next infusion, study intervention may be continued.
2. If a Grade 2 treatment-related TEAE does not resolve to Grade ≤ 1 by the day before the next infusion, but it is manageable and/or not clinically relevant, the Medical Monitor should be consulted to assess if it is clinically reasonable to administer the following infusion.

Note that treatment recommendations regarding continuation, hold, or discontinuation by grade are different depending on the specific toxicity (see [Appendix 5](#)). Toxicity grading is assigned based on NCI-CTCAE v5.0.

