1.0 Skin Toxicities	
	For mucous membrane involvement of SJS or TEN, appropriate consulting services should be offered to guide management in preventing sequelae from scarring (e.g, ophthalmology; ear, nose, and throat; urology; gynecology; etc, as appropriate)
G4: Skin erythema and blistering/sloughing covering $\geq 10\%$ to $> 30\%$ BSA with associated signs (e.g, erythema, purpura, epidermal detachment, mucous membrane detachment) and/or systemic symptoms and concerning associated blood work abnormalities (e.g, liver function test elevations in the setting of DRESS/DIHS)	
Permanently discontinue ICPI
 
Admit patient immediately to a burn unit or ICU with consulted dermatology and wound care services
 
Consider further consultations based on management of mucosal surfaces (e.g, ophthalmology; urology; gynecology; ear, nose, and throat surgery; etc) Initiate IV (methyl)prednisolone (or equivalent) 1-2 mg/kg, tapering when toxicity resolves to normal
 
IVIG or cyclosporine may also be considered in severe or corticosteroid-unresponsive cases
 
Consider pain/palliative consultation and/or admission in patients presenting with DRESS manifestations

Additional considerations: The usual prohibition of corticosteroids for SJS is not relevant here, as the underlying mechanism is a T-cell immunodirected toxicity
 
Adequate suppression is necessary with corticosteroids or other agents and may be prolonged in cases of DRESS/DIHS
 
All recommendations are expert consensus based, with benefits outweighing harms, and strength of recommendations are moderate
	

Abbreviations: ADL, activities of daily living; AE, adverse event; BSA, body surface area; CBC, complete blood count; CTCAE, Common Terminology Criteria for Adverse Events; DIHS, drug-induced hypersensitivity syndrome; DRESS, drug reaction with eosinophilia and systemic symptoms; G, Grade; ICPI, immune checkpoint inhibitor; ICU, intensive care unit; irAE, immune-related adverse event; IV, intravenous; IVIG, intravenous immunoglobulin; NA, not applicable; SCAR, severe cutaneous adverse reactions; SJS, Stevens-Johnson syndrome; TEN, toxic epidermal necrolysis.

Table A2

Management of GI irAEs in Patients Treated With ICPis

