8.5 Lymphopenia	
Definition: An abnormally low level of lymphocytes in PB; for adults, counts of < 1,500/mm ³	
Diagnostic work-up	
History and physical examination (special attention for lymphocyte-depleting therapy such as fludarabine, ATG, corticosteroids, cytotoxic chemotherapy, radiation exposure, etc, as well as history of autoimmune disease, family history of autoimmune disease) Evaluation of nutritional state as cause	
Spleen size	
CBC with differential, peripheral smear and reticulocyte counts	
CXR for evaluation of presence of thymoma	
Bacterial cultures and evaluation for infection (fungal, viral, bacterial specifically CMV/HIV)	
Grading	Management
G1-2: 500-1,000 PB lymphocyte count	Continue ICPi for G1 to G2
G3: 250-499 PB lymphocyte count	For G3 single laboratory values out of normal range without any clinical correlates, hold treatment until resolution to G1
G4: < 250 PB lymphocyte count	For G4, for single laboratory values out of normal range without any clinical correlates, permanent treatment discontinuation is not required. Treatment should be held until the etiology is determined. Permanent treatment discontinuation will only be required, if lymphopenia is considered of immune-related in nature, no clear alternative explanation exists for the event, and grade 4 lymphopenia does not resolve within 14 days. If the event is not considered immune-related and resolves to G \leq 1 restarting treatment may be considered.

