8.0 Hematologic Toxicities	
	
Check CBC weekly for monitoring, initiation of CMV screening Consider holding ICPi
 
Initiate Mycobacterium avium complex prophylaxis and Pneumocystis jirovecii prophylaxis, CMV screening. HIV/hepatitis screening if not already done
 
May consider EBV testing if evidence of lymphadenopathy/hepatitis, fevers, hemolysis consistent with lymphoproliferative disease.

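### Protocol Appendix 5, Table A1: every Grade 3 severe cutaneous reaction meets both a discontinue and a hold instruction, and the two carry different consequences for restarting and recording

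*Protocol*

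**What the plan says.** Protocol Appendix 5, Table A1, item 1.3 covers SCARs, including Stevens-Johnson syndrome (SJS) and toxic epidermal necrolysis. Three of its rows matter here.

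- **All Grades:** "In cases of suspected SJS or any mucous membrane involvement, discontinue ICPi treatment and monitor closely for improvement, regardless of grade".
- **Grade 3:** the definition opens "G3: Skin sloughing covering < 10% BSA with mucosal involvement associated signs", and the action is "Hold ICPi therapy and consult with dermatology".
- **Grade 4:** "Permanently discontinue ICPI".

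Protocol 6.8 closes by saying that "treatment recommendations regarding continuation, hold, or discontinuation by grade are different depending on the specific toxicity", and refers to Appendix 5. It thus names hold and discontinuation as separate actions.

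On a secondary matter, Table A8, item 8.5 (lymphopenia) says: "For G3 single laboratory values out of normal range without any clinical correlates, hold treatment until resolution to G1". For a Grade 4 value of the same kind it says dosing is held while the cause is sought. After a page break, with no grade label, comes the line "Consider holding ICPi". Section 6.8 has a general sentence: "Single laboratory values out of the normal range that do not have any clinical correlation do not necessarily need treatment interruption".

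**The concern.** A site with a Grade 3 SCAR in front of it finds two instructions in the same table, and the words differ. If the words meant the same thing, this would be untidy drafting and no more. They may not, because elsewhere the protocol and SAP attach separate procedures and separate reporting categories to stopping and to pausing study drug. At stake is whether a participant with a mucosal skin reaction may be dosed again, through which approvals, and under which action the event appears in the safety data.

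**Working it through.** No arithmetic applies and the plan gives no figure to reproduce. The check sets the passages side by side.

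**Step 1: do the two triggers overlap?** The All Grades trigger is suspected SJS or any mucosal involvement, at any grade. The Grade 3 definition contains mucosal involvement. Every case that fits the Grade 3 definition therefore also fires the All Grades row. The overlap is complete by definition and does not depend on how often such cases occur.

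**Step 2: what does each reading of *discontinue* do to the Grade 3 row?**

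| Reading of the All Grades row | Effect on the Grade 3 hold |
|---|---|
| Stop for now | Same action as the hold; the rows agree |
| End study treatment | The hold never applies on its own, because no Grade 3 case lies outside the All Grades trigger |

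The table does not say which reading is meant.

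**Step 3: do the documents treat the two actions differently?**

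| | Discontinuation | Hold |
|---|---|---|
| Visit (Protocol 7.1) | End-of-Treatment visit on the day of withdrawal or within 7 days | None attached |
| Restart (Protocol 7.1.2.1) | One course only, at the investigator's discretion and with agreement of the Medical Responsible; new baseline scan; haematology and chemistry from within 2 weeks | None of these steps attached |
| Coding (SAP 15.1) | Action taken: drug withdrawn; counted as permanent discontinuation | Action taken: drug interrupted; counted as temporary discontinuation |

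SAP 15.1.2 tabulates the two categories separately.

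**Step 4: does another section settle it?** Section 6.8 sends specific Grade 3 immune-related events to Appendix 5. Section 6.9.2 says only that drug is generally suspended at Grade 3, and its list of mandatory permanent stops is for Grade 4 events. The Grade 3 SCAR row gives no condition for resuming. The Grade 3 rows for rash (1.1) and bullous dermatoses (1.2) do: there dermatology is consulted on whether resuming is appropriate.

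**Step 5: lymphopenia.** Laboratory-only Grade 3 has one explicit instruction in Table A8, which is to hold. The ungraded line follows the Grade 4 text. Read with Grade 4, it softens an instruction already given there; read with Grade 3, it softens that one. The table layout was lost in text extraction, so its row cannot be fixed from the text available.

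**The case against.** The strongest reply is that *discontinue* in the All Grades row need not be permanent. It is paired with watching for improvement. The same table says so expressly at Grade 4 when it means a permanent stop, and the Guillain-Barré rows in Table A7 draw the same line between Grade 2 and Grades 3-4. Section 6.8 speaks of transient as well as permanent discontinuation, section 7.1.1 is headed as temporary discontinuation, and the Grade 3 aplastic anaemia text uses the word for a stop that ends on recovery. This stands. A reader might infer that the table orders dosing to stop at one site and continue at another. It does not: both rows stop dosing immediately. Nor does discontinuation bar all later dosing, since 7.1.2.1 permits one reinitiation after an adverse event. What remains open is whether and how dosing resumes.

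A second reply is that the words about grade in the All Grades row make it the overriding rule. That is a fair reading, but under the stronger sense of *discontinue* it leaves the Grade 3 hold with no case of its own, so the row still needs correcting.

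On lymphopenia, three stronger inferences are tempting, and the documents do not support them.

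- **That Appendix 5 contradicts itself for laboratory-only Grade 3.** It gives one explicit instruction for that case. The ungraded line most naturally continues Grade 4, and the 6.8 sentence is permissive and general, while 6.8 itself defers to toxicity-specific guidance.
- **That the hold has no end, because inclusion criterion 8a sets no lymphocyte minimum.** Section 6.8 makes a Grade 2 or 3 adverse reaction that has not recovered to Grade 0-1 within 12 weeks of the last dose an indication for permanent discontinuation. Exclusion criterion 8 also bars persisting toxicity above Grade 1 from prior therapy.
- **That exposure counts in a 29-participant trial are materially distorted.** No event rates are given, two missed doses for an adverse event already prompt consultation with the Medical Monitor, and SAP 4.1 records early discontinuation of the study, a low number of participants and no efficacy analyses.

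**Conclusion.** The SCAR point holds in a limited form. All Grade 3 SCARs as defined meet both a discontinue and a hold instruction, and the table does not say whether the first is permanent or temporary. Dosing stops either way. The participant's route back to treatment, and the SAP category in which the event is counted, depend on which word a site follows. The conclusion rests on reading the Grade 3 definition as requiring mucosal involvement, which is its plain sense. How many participants this could affect cannot be stated, because the documents give no frequency. No sample-size, power or alpha figure is touched. The case for correction is clarity of a safety instruction, and does not rely on any effect on trial results.

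The lymphopenia matter is minor: one ungraded line sits uneasily with firmer hold instructions, and the link to the general sentence in 6.8 could be stated more directly.

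**What to change.** The sponsor's medical team should do the following.

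1. Reconcile the All Grades and Grade 3 rows of Table A1, item 1.3, so that one instruction applies to a Grade 3 SCAR.
2. State whether *discontinue* in the All Grades row is permanent or temporary, and whether the reinitiation procedure in 7.1.2.1 applies afterwards. The matching action-taken category for the SAP then follows.
3. As a minor item, label the grade to which the "Consider holding ICPi" line in Table A8, item 8.5 belongs, and say whether that table takes precedence over the single-laboratory-value sentence in 6.8 or is to be reconciled with it.

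This review does not say which clinical instruction is right. The cost is a protocol amendment or clarification letter, wording only, with no change to the design or analyses. Given the early discontinuation recorded in SAP 4.1, it matters for any participant still on study drug, on which the documents are silent, and for any reuse of these tables.
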